5.5 Visit rescheduling

Visits may be rescheduled within the visit window established in the SoA (Table 1). If a visit needs to be rescheduled outside the pre-specified visit window and the participant did not meet any of the conditions specified in Sections 5.5.1, 5.5.2 and 5.5.3 below, the case should be discussed with the AstraZeneca Study Physician and documented in the ISF. Extension of the run-in period for a participant for any other reason may only be allowed upon approval of the AstraZeneca Study Physician.

5.5.1 Participants who do not meet criteria at Visit 1

Participants who do not meet the criteria at Visit 1 (Section 5.2.2) are not allowed to proceed with any study baseline assessments and Visit 1 should be rescheduled to a timepoint where participants can fulfil these criteria. For acute asthma exacerbation or acute upper or lower respiratory tract infection, refer to Section 8.3.

5.5.2 Participants who are unable to come for Visit 1

Visit 1 should be rescheduled as soon as possible, or when considered safe as judged by the Investigator in the following transient situations/reasons:

- Including, but not limited to, study-supplied equipment failure, unforeseen personal events that mandate missing Visit 1, etc.
- Civil crisis, natural disaster, or public health crisis.

5.5.3 Visits 2, 3 and 4, and Follow-up

In general, Visits 2, 3, and 4, and the follow-up may be re-scheduled within the respective visit windows established in the SoA (Table 1). Rescheduling of visits beyond the visit window indicated in the SoA (Table 1) should be an exception and the reason should be recorded in the ISF.

5.5.4 COVID-19 positive test

COVID-19 testing should follow prevailing local guidelines at the time of the COVID-19 testing procedure and participants are considered as having positive COVID-19 test when they fulfill the criteria defined as per aforementioned local guidelines.

Participants who have a positive COVID-19 test and are asymptomatic (or have mild disease without lower respiratory tract symptoms – per investigator's judgement) are allowed to have the visits rescheduled as follows:

- Participants who have a positive COVID-19 test immediately before Visit 1 *AND* are asymptomatic: delay Visit 1 up to 14 days (in accordance with local guidelines for quarantine and re-testing procedure) from the date when the test was performed.
- Participants who have a positive COVID-19 test immediately before Visit 2 or Visit 3 *AND* are asymptomatic should receive the study intervention drug within the allowed visit window established in the SOA (Table 1).
- Participants who have a positive COVID-19 test immediately before Visit 4 *AND* are asymptomatic: delay Visit 4 up to 14 days (in accordance with local guidelines for quarantine and re-testing procedure) from the date when the test was performed.

Participants with any moderate or severe COVID-19 disease, or COVID-19 disease with lower respiratory tract symptoms, irrespective of severity, at any time during the study period shall be discontinued (see Section 7.1).

In case the reason for postponing is an acute exacerbation or respiratory tract infection, refer to Section 8.3 for instructions.

6 STUDY INTERVENTION

Study intervention is defined as any investigational intervention(s), marketed product(s) or placebo intended to be administered to or medical device(s) utilized by a study participant according to the study protocol.

6.1 Study Intervention(s) Administered

6.1.1 Investigational Products

Arm name	Benralizumab
Intervention name	Benralizumab (Fasenra)
Туре	Combination Product
Dose formulation	Single-use pre-filled syringe (injection) One mL solution in a single-use pre-filled syringe made from type I glass with a staked 29-gauge ¹ / ₂ -inch (12.7 mm) stainless steel needle, rigid needle shield, and Fluorotec-coated plunger stopper in a passive safety device.
Unit dose strength(s)	30 mg
Dosage level(s)	3 doses, once every 4 weeks (at baseline [V1], week 4 [V2] and week 8 [V3])
Route of administration	Subcutaneous
Use	Other (Phase 4) - Treatment of severe asthma per current approved USPI and EU SmPC/European Public Assessment Report (EPAR)
IMP and NIMP	IMP
Sourcing	Provided centrally by the sponsor; manufactured by AstraZeneca AB
Packaging and labelling	Study Intervention will be provided in pre-filled syringe. Each pre-filled syringe will be labelled in accordance with Good Manufacturing Practice (GMP) Annex 13 and as required per country regulatory requirement. Label text will be translated into local languages as required
[Current/former name(s) or alias(es)]	MEDI-563

6.1.2 Medical Devices

6.1.2.1 Benralizumab pre-filled syringe

- 1) The AstraZeneca manufactured medical devices (or medical devices manufactured for AstraZeneca by a third party) provided for use in this study are,
 - Syringe prefilled with benralizumab (Status, US FDA and EMA approved)

- 2) Instructions for medical device use are provided in Product Full Prescribing Information / Product Package Leaflet, Product Instructions for Use in the local language (for home administration) and/or patient information leaflet.
- 3) All medical device deficiencies (including malfunction, use error and inadequate labelling) shall be documented and reported by the investigator throughout the clinical investigation (see Section 8.4.10) and appropriately managed by the sponsor.

6.1.2.2 Respiratory Gating Device

- 1) The Geratherm Respiratory manufactured medical devices (or medical devices manufactured for Geratherm Respiratory by a third party) provided for use in this study are,
 - Spirotik (Status, CE-marked [according to Medical Device directive])

This is a portable spirometer that comes with disposable mouth pieces and nose clips, and operates through a software, Blue Cherry (Geratherm Respiratory), using a laptop. This device will be used to monitor participants' breathing during the CT scan procedure to ensure CT scans are taken at the correct breathing level.

- 2) Instructions for medical device use are provided in a separate CT scan manual and ecourse materials provided by a central vendor.
- 3) All medical device deficiencies (including malfunction, use error and inadequate labelling) shall be documented and reported by the investigator throughout the clinical investigation (see Section 8.4.10) and appropriately managed by the sponsor.

6.2 Preparation/Handling/Storage/Accountability

- 1) The investigator or designee must confirm appropriate temperature conditions have been maintained during transit for all study intervention received and any discrepancies are reported and resolved before use of the study intervention.
- 2) Only participants enrolled in the study may receive study intervention and only authorized site staff may supply or administer study intervention. All study intervention must be stored in a secure, environmentally controlled, and monitored (manual or automated) area in accordance with the labelled storage conditions with access limited to the investigator and authorized site staff.
- 3) The investigator, institution, or the head of the medical institution (where applicable) is responsible for study intervention accountability, reconciliation, and record maintenance (i.e., receipt, reconciliation, and final disposition records).
- 4) Further guidance and information for the final disposition of unused study interventions are provided in the Pharmacy Manual.

The IP will be administered at the study site on Visit 1, 2 and 3. IP will be supplied to the site in a kit with a single-use pre-filled syringe of benralizumab. Dosing should be performed following the completion of all visit assessments for Visit 1, 2 and 3.

All shipments of IP include a data logger which will allow the Investigator or designee to confirm appropriate temperature conditions have been maintained during transit for all study treatment received and any discrepancies are reported and resolved before the use of the study treatment. Only participants enrolled in the study may receive study treatment and only authorized site staff may supply the study treatment.

Only authorized site staff may administer the study treatment.

Before investigational product administration

Prior to each IP administration:

- 1) The Investigator/authorized delegate will assess the injection site as per the standards of medical care.
- 2) For WOCBP, a urine pregnancy test will be performed; IP will be administered only if the result of the test is negative.

Investigational product administration

The IP will be administered by the Investigator/authorized delegate. Investigational product at a dose of 30 mg should be administered SC using the pre-filled syringe into the upper arm, thighs, or the abdomen (see Figure 2). It is suggested that the site of injection is rotated such that the participant receives IP at a different anatomical site at each treatment visit. Investigational product should not be administered into areas where the skin is tender, bruised, erythematous, infected or hardened, or where there is an open graze.

Figure 2Suggested schema of injection sites

Further details on IP administration are described in the IP Handling Instruction provided to study sites. Investigational product administration must be carried out in line with the Instruction.

After investigational product administration

Participants should be observed according to clinical practice after administration of IP for the appearance of any acute drug reactions.

Conditions requiring investigational product administration rescheduling

Administration of the IP may only be rescheduled if:

- 1) Rescheduled date of IP administration falls within the visit window indicated in the SoA.
 - Note: Dose interruptions requiring rescheduling of IP administration outside the visit window indicated in the SoA are not permitted (see Section 7.1.1 for further details).
- 2) Participant needs to reschedule Visit 1 per Section 5.5.1 and 5.5.2 (see Section 5.5 for further details).

6.3 Measures to Minimize Bias: Randomization and Blinding

The current study is an open-label study with no blinding at site level.

6.4 Study Intervention Compliance

The administration of all study treatments should be recorded in the appropriate section of the electronic Case Report Form (eCRF). The study treatment provided for this study will be used only as directed in this CSP. The study treatment will be administered at the study site on treatment visits (Visit 1, 2 and 3) as specified in the SoA (Table 1). Participants who cannot

receive the first study treatment at Visit 1 as described in Section 5.5.1 and 5.5.2 may be rescheduled (see Section 5.5 for further information). The second and third study treatment must be administered within the visit window as specified in the SoA (Table 1). Any change from the dosing schedule (dose interruptions or dose discontinuations) should be recorded in the eCRF. It should be noted that dose modifications are prohibited and will be considered as a discontinuation of study intervention.

The participants will receive study intervention directly from the investigator or designee, under medical supervision. The date, and time if applicable, of dose administered in the clinic will be recorded in the source documents and recorded in the eCRF. The dose of study intervention and study participant identification will be confirmed at the time of dosing by a member of the study site staff other than the person administering the study intervention. Study site personnel will examine the pre-filled syringe to ensure that the study intervention was administered completely.

Intervention start and stop dates, including dates for intervention delays and/or dose reductions will also be recorded in the eCRF.

6.5 Concomitant Therapy

The participants' ICS or OCS and additional asthma maintenance medication at enrolment will remain unchanged during the run-in and treatment period. Maintenance and rescue asthma medications are not regarded as an IP and will not be provided/reimbursed by AstraZeneca.

To satisfy inclusion criterion #3, a history of continuous treatment with high-dose ICS and LABA for \geq 3 months prior to Visit 0 (V0), with or without oral corticosteroids and additional asthma controllers should be documented in source and recorded in the eCRF at Visit 0 (V0). If the participant is taking ICS plus LABA, the ICS and LABA can be parts of a combination product or given by separate inhalers. The ICS dose must be > 500 µg/day fluticasone propionate dry powder formulation or equivalent daily. For ICS/LABA combination preparations, the highest approved maintenance dose in the local country will meet this ICS criterion.

In order to satisfy inclusion criterion #4, a history of OCS therapy (prednisone ≥ 5 mg/day for ≥ 3 continuous months directly preceding Visit 0 (V0) and stable OCS dosage for ≥ 4 weeks before Visit 0 (V0) should be documented in source and recorded in the eCRF at Visit 0 (V0). Alternate OCS dosing (e.g., every other day), other dosing frequencies, and OCS therapy other than prednisone/prednisolone are allowed provided the average daily dose is equivalent to ≥ 5 mg of prednisone. Participants should also remain on stable OCS dosing for the duration of the study.

In order to satisfy inclusion criterion #10, participants are required to remain on a stable

asthma treatment regimen apart from the use of rescue medication including the use of any other asthma medication for at least 3 months prior to Visit 0 (V0). The Investigator will record information on background therapy compliance during the study in the eCRF.

All medications taken in the 3 months prior to Visit 0 (V0) and throughout the study must be recorded in the eCRF along with the reason for treatment by the Investigator/authorized delegate at each visit, as specified in Table 1.

Any medication or vaccine (including over-the-counter or prescription medicines, vitamins, and/or herbal supplements) or other specific categories of interest that the participant is receiving at the time of enrolment or receives during the study must be recorded along with:

Reason for use

- Dates of administration including start and end dates
- Dosage information including dose and frequency

The Study Physician should be contacted if there are any questions regarding concomitant or prior therapy.

Medication/class of drug	Usage (including limits for duration permitted and special situations
Maintenance treatment with ICS and LABA (including ICS/LABA	No changes in either dose or regimen are allowed from screening visit (V0) and throughout the IP treatment.
combinations)	Budesonide/Formoterol "MART" reliever therapy is allowed as rescue medication and its use as a rescue medication will be recorded in the eCRF.
	Twice daily BDs should be withheld for at least 12 hours prior to Visit 0, 1 and 4 at the site.
	Once daily BDs should be withheld for at least 24 hours prior to Visit 0, 1 and 4 at the site.
Maintenance treatment with LAMA (isolated or in combinations)	No changes in either dose or regimen are allowed from screening visit (V0) and throughout the IP treatment.
	Twice daily LAMAs should be withheld for at least 12 hours prior to Visit 0, 1 and 4 at the site.
	Once daily LAMAs should be withheld for at least 24 hours prior to Visit 0, 1 and 4 at the site.
CCI	CCI CCI

Table 4Restricted medicines

Medication/class of drug	Usage (including limits for duration permitted and special situations
Short-acting muscarinic antagonist (SAMA)	SAMA is allowed as rescue medication. SAMA should be withheld for at least 12 hours prior to Visit 0, 1 and 4 at the site.
CCI /SAMA combinations	 CCI /SAMA combination is allowed as rescue medication. CCI /SAMA combination should be withheld for at least 12 hours prior to Visit 0, 1 and 4 at the site.
Additional maintenance controllers	Leukotriene receptor antagonists (LTRA) should be restricted for at least 24 hours prior to the scheduled spirometry test at Visit 0 (V0), and prior to scheduled Visit 1 and 4, at the site. Twice daily theophyllines should be withheld for at least 12 hours prior to Visit 0, 1 and 4 at the site. Once daily theophyllines should be withheld for at least 24 hours prior to Visit 0, 1 and 4 at the site.
Intranasal steroid	Intranasal steroid is allowed at the discretion of the Investigator.
Chronic immunosuppressive medication (including corticosteroids) or any experimental anti-inflammatory therapy	Not allowed within 3 months prior to Visit 0 (V0) as per exclusion criterion #14. Chronic oral corticosteroids for asthma are allowed as per Section 5.1, inclusion criterion #3 Topical administration of immunosuppressive medication may be administered at the Investigator's discretion as clinically indicated.
Allergen immunotherapy	Allowed if on stable therapy for at least 30 days prior to Visit 0 (V0), with no anticipated change during the study. The participant should not receive an allergen immunotherapy injection on the same day as the IP administration.
Inactive/killed vaccinations	Receipt is allowed provided they are not administered within 7 days before/after any IP administration.

Table 5	Prohibited	medicines

Prohibited medication/class of drug:	
Immunoglobulin or blood products	Use prohibited within 30 days prior to visit 0 (V0). Immunoglobulin is not allowed during the study except for treatment of an AE, as judged by the Investigator.
Marketed or investigational biologic (monoclonal or polyclonal antibody)	Use prohibited within 4 months or 5 half-lives (whichever is longer) prior to Visit 0 (V0), and during the study.
Live/attenuated vaccines	Use prohibited 30 days prior to Visit 0 (V0), during the treatment period, and for 12 weeks after the last dose of the IP.
Previously received benralizumab	Prohibited.

Prohibited medication/class of drug:	
Any other Investigational product	Use prohibited within 30 days or 5 half-lives (whichever is longer) prior to Visit 0 (V0) and during the study.
Oral or ophthalmic non-selective β- adrenergic antagonist	Use prohibited as per inclusion criterion #14 unless it does not interfere with study conduct, influence the interpretation of study observations/results, or put the participant at increased risk during the study.
Change to allergen immunotherapy or new allergen immunotherapy	Use prohibited within 30 days prior to visit 0 (V0).
Over-the-counter inhaled epinephrine	Use prohibited.

Paracetamol/Acetaminophen, at doses of ≤ 2 grams/day, is permitted for use any time during the study. Other concomitant medications not excluded based on inclusion criterion #14 and exclusion criteria #12 to #14, #16 and #17 are permitted for use any time during the study (see Section 5.1 and 5.2.1).

Table 6Other prohibited treatments

Prohibited treatments	
Lung volume reduction surgery	Prohibited
Lung resection	Prohibited
Thermal bronchoplasty	Prohibited
Pulmonary rehabilitation	Active phase of rehabilitation is prohibited prior to screening and through the study

6.5.1 Rescue Medicine

The sponsor will not supply any rescue medication.

Rescue use of medications administered via nebulization is discouraged, except as urgent treatment during an asthma exacerbation. Occasions where medications are administered via nebulization will be recorded separately from metered dose inhaler inhalations.

The following rescue medications may be used:

- Short-acting muscarinic antagonists (SAMAs)

- Short-acting muscarinic antagonists (SAMAs) should be withheld for at least 12 hours prior to Visit 0, 1 and 4 at the site.
- CCI and SAMA combinations
 - CCI /SAMA combinations should be withheld for at least 12 hours prior to Visit 0, 1 and 4 at the site.
- Maintenance and reliever therapy (MART)
 - MART reliever therapy and the use of Budesonide/formoterol as a rescue medication are allowed at the Investigator's discretion. Total ICS dose of MART maintenance therapy and whether it is used as rescue medication will be recorded in the eCRF.
 - MART reliever therapy should be withheld for at least 12 hours prior to Visit 0, 1 and 4 at the site (Table 4).
- Oral corticosteroids (OCS)
 - OCS use for the treatment of asthma exacerbation is allowed for the duration of ≤ 4 weeks. Longer treatment with OCS should be discussed with the AZ Study Physician to decide on the participant's disposition. Please refer to Section 8.3.1 for further instructions on study procedures in case of acute asthma exacerbation or respiratory tract infection.

6.6 Dose Modification

This protocol does not permit dose modification (see Section 4.3). Dosing can only be discontinued due to an AE per the Investigator's clinical judgement or unforeseen circumstances (see Section 7.1).

Any change from the dosing schedule (dose interruptions or dose discontinuations) should be recorded in the eCRF.

6.7 Intervention After the End of the Study

The investigator will discuss the available treatment options with participants who complete the study or who withdraw early from the study. The sponsor will not provide benralizumab upon study completion or early study withdrawal.

7 DISCONTINUATION OF STUDY INTERVENTION AND PARTICIPANT DISCONTINUATION/WITHDRAWAL

Procedures for E/D follow-up should be followed as specified in SoA and the participant will be withdrawn from the study.

Note that discontinuation from study intervention is NOT the same thing as a withdrawal from the study.

If a participant has no baseline assessments which are successfully performed (PROs, CT scan or Spirometry) then the participant must be withdrawn from the study. Procedures and study intervention should be discontinued.

See the SoA (Table 1) for data to be collected at the time of intervention discontinuation and follow-up and for any further evaluations that need to be completed.

7.1 Discontinuation of Study Intervention

It may be necessary for a participant to permanently discontinue study intervention. If study intervention is permanently discontinued, the participant will remain in the study to be evaluated for safety and, if he/she had completed the study procedures at Visit 1 and have had at least one dose of the study intervention, baseline measurements will also be evaluated.

If a participant discontinued study intervention, procedures for an Early Study Intervention Discontinuation (E/D) follow-up should be followed as described in the SoA. Refer to Table 1 for data to be collected at the time of discontinuation of study intervention and follow-up and for any further evaluations that need to be completed

Participants may be discontinued from IP in the following situations.

- Participant decision. The participant is at any time free to discontinue treatment, without prejudice to further treatment (see Section 7.2).
- An AE that is considered to jeopardize the safety of a participant participating in the study as judged by the Investigator or AstraZeneca.
- Positive pregnancy test at any time during the study (see Section 8.4.8 Pregnancy), or breastfeeding.
- Severe non-compliance with the CSP.
- Development of any study-specific criteria for discontinuation, including:
 - An anaphylactic reaction to the IP,
 - A helminth parasitic infestation requiring hospitalization,
 - An asthma-related event

- o requiring hospitalization for more than 24h or intubation,
- requiring OCS treatment after week 11 (see Section 8.3.1 for further details)
- Any new or recurrent malignancy, except non-melanoma skin cancers,
- -19
 - Moderate or severe disease at any time during the study period.
 - Mild disease with lower respiratory tract symptoms at any time during the study period.
 - Mild disease without lower respiratory tract symptoms may continue in the study at the investigator's discretion and visits rescheduled per Section 5.5.4.
 - Asymptomatic patients with COVID-19 positive test should not be discontinued and visits rescheduled per Section 5.5.4.

For details relating to dose modifications, see Section 6.6.

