8.3 Asthma Exacerbations and Respiratory Tract Infections

Acute asthma exacerbation, respiratory tract infections and their treatments may alter the inflammatory profile of the airways. The assessment for acute exacerbation and other acute respiratory tract infection should therefore occur before any other assessments are performed.

During the study, an asthma exacerbation will be defined as a worsening of asthma that leads to any of the following:

- Use of systemic corticosteroids (or a temporary increase in a stable oral corticosteroid background dose) for at least 3 days; a single depo-injectable dose of corticosteroids will be considered equivalent to a 3-day course of systemic corticosteroids.
- An emergency room/urgent care visit (defined as evaluation and treatment for < 24 hours in an ER or urgent care center) due to asthma that required systemic corticosteroids (as per above).
- An inpatient hospitalization due to asthma (defined as an admission to an inpatient facility and/or evaluation and treatment in a healthcare facility for ≥ 24 hours).

The start of an exacerbation is defined as the start date of systemic corticosteroids, date of ER or urgent care visits requiring systemic corticosteroids, or date of hospital admission due to asthma, whichever occurs earlier.

The end date of an exacerbation is defined as the last date of systemic corticosteroids, return to baseline dose of OCS for those on chronic OCS, date of ER or urgent care visit, or date of hospital discharge, whichever occurs later.

8.3.1 Study Visit Procedures Following Determination of An Acute Asthma Exacerbation or Respiratory Tract Infection

All asthma exacerbations that occur during the treatment and study period must be recorded in the exacerbation eCRF. Asthma exacerbation should be recorded as an AE only if it fulfils any of the criteria for SAE (Section 8.4.7), or the AE leads to IP discontinuation.

Participants who have an asthma exacerbation (worsening of asthma) or respiratory tract infection requiring hospitalization (defined as an admission to an inpatient facility and/or evaluation and treatment in a healthcare facility for \geq 24 hours e.g., an ER or urgent care

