center) will be discontinued from the study (see Section 7.1) and procedures for an Early Study Intervention Discontinuation (E/D) follow-up should be followed as described in the SoA. (Refer to Table 1 for data to be collected at the time of discontinuation of study intervention and follow-up and for any further evaluations that need to be completed).

Participants who have an asthma exacerbation (worsening of asthma) or respiratory tract infection that does not require hospitalization (defined above), but require use of antibiotics and/or systemic corticosteroids (or a temporary increase in a stable oral corticosteroid background dose) for at least 3 days [a single depo-injectable dose of corticosteroids will be considered equivalent to a 3-day course of systemic corticosteroids] should have their visit schedule adjusted per the following guidance, according to when it occurs:

- Before Visit 1 (V1), this visit should be rescheduled to occur after resolution of the exacerbation/infection and at least 4 weeks after the last dose of any medication to treat the exacerbation/infection, provided that there are no safety concerns as judged by the Investigator.
- Between Visit 1 (V1) and Visit 3 (V3), there will be no changes to the study activities and the SoA should be followed (Table 1).
- Between Visit 3 (V3) and Visit 4 (V4), the participant will be permitted to undergo the study assessments for Visit 4, but it should be delayed to ensure an interval between Visit 4 and the last dose of antibiotic or OCS, whichever ends later (or return of OCS dose to previous maintenance dose) of at least 7 days, but no longer than 14 days, per investigator's discretion.

In case of uncertainty related to procedures following an exacerbation, please consult with the AstraZeneca US study team.

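### Section 7.1 allows discontinuation for OCS after week 11, but Section 8.3.1, which it cites, has no such rule and permits a delayed Visit 4, so the week 13 scan depends on which section is followed

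*Protocol*

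**What the plan says.** Protocol Section 7.1 opens its list permissively: "Participants may be discontinued from IP in the following situations". Among the study-specific criteria it names an asthma-related event "requiring OCS treatment after week 11 (see Section 8.3.1 for further details".

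Section 8.3.1 discontinues hospitalised cases. It then covers non-hospitalised exacerbations or respiratory infections that need antibiotics and/or at least 3 days of systemic corticosteroids. For such an event between Visits 3 and 4, "the participant will be permitted to undergo the study assessments for Visit 4, but it should be delayed" until at least 7 and at most 14 days after the last antibiotic or OCS dose, or after return to the maintenance OCS dose. It gives no week-11 cut-off. It ends by telling sites to ask the sponsor's study team when in doubt.

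Section 6.5.1 allows OCS for an exacerbation for up to 4 weeks and also refers to 8.3.1, again with no week-11 limit.

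Dosing in Section 6.1.1 is "3 doses, once every 4 weeks (at baseline [V1], week 4 [V2] and week 8 [V3". In the Schedule of Activities, the E/D column has neither CT nor spirometry.

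On what follows discontinuation, three places differ:
- Section 1.1 counts anyone who stops benralizumab as withdrawn from the study.
- Section 7 says "Procedures for E/D follow-up should be followed as specified in SoA and the participant will be withdrawn from the study", and its next sentence says that stopping the intervention is not the same as withdrawing.
- Section 7.1 keeps the participant in the study for safety evaluation.

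**The concern.** A cross-reference for further details should lead to the rule that it abbreviates. This one leads to a section that treats the same participant differently. A site working from 7.1 may send a participant who starts OCS in week 12 to the E/D visit. A site working from 8.3.1 would wait for the course to end and then do the Visit 4 assessments. No passage says which section prevails.

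At stake is whether the scan that carries the primary endpoint is done. The SAP (Sections 3.2.1 and 3.2.2) analyses change in mucus volume and in the secondary imaging parameters in both the Evaluable set and the primary analysis population. The primary analysis population already excludes exacerbators, so for these change analyses only the Evaluable set keeps them. SAP Table 3 promises inclusion whether or not treatment was discontinued, but a participant sent down the E/D path has no week 13 scan to include.

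**Working it through.** **1. Does the 7.1 criterion have a dose to stop?** Visit 1 is day 0. The third and last planned dose is at week 8 ± 5 days, which is 56 ± 5 = days 51 to 61. Week 11 is day 77. On the planned schedule all doses have been given before the criterion can apply. Its practical effect therefore comes through the E/D path.

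**2. Do the two rules cover the same participant?** Visit 4 is at week 13 ± 5 days, which is 91 ± 5 = days 86 to 96. A course that starts on day s and lasts d days ends on day s + d − 1. Section 8.3.1 then places Visit 4 between day s + d + 6 and day s + d + 13. The earliest permitted Visit 4 is inside the window when s + d + 6 ≤ 96, that is s ≤ 90 − d.

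| Course length d (days) | Permitted Visit 4 if s = 78 | Start days after week 11 that allow an in-window Visit 4 |
|---|---|---|
| 3 | days 87–94 | 78–87 |
| 5 | days 89–96 | 78–85 |
| 7 | days 91–98 | 78–83 |
| 10 | days 94–101 | 78–80 |
| 14 | days 98–105 | none |

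The overlap is real: after short courses that begin after week 11, 8.3.1 yields a Visit 4 on schedule. Longer courses push it past day 96, but SAP Addendum Section 1.2 removes the Visit 4 window, so those scans would be analysed as well.

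**3. Which analyses can move?**
- *Primary analysis population.* A course of at least 3 days for worsening asthma meets the exacerbation definition in Section 8.3, so the participant is excluded under either reading. A course under 3 days meets 7.1 but, with no other criterion met, is neither an exacerbation nor covered by 8.3.1. Only in that case could following 7.1 change this population.
- *Evaluable set.* SAP Addendum Section 1.1 now asks for post-treatment data in at least one of PROs, CT or spirometry. The PRO rows of the schedule are redacted, so it cannot be seen whether an E/D participant would stay in the set. Under Addendum Section 2.14, a participant without a week 13 value is in any case dropped from the analysis of that parameter.

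**4. How many participants?** The stated flow in Section 1.1 is 38 enrolled, 34 evaluable and 29 in the primary analysis population. The derivation in Section 9.2 is redacted, so only the differences can be used.
- Evaluable minus primary: 34 − 29 = 5, and 5/34 = 14.7%.
- Weeks 11 to 13 are 2 of 13 weeks. If all 5 were OCS-treated, non-hospitalised exacerbations spread evenly over time, 5 × 2/13 = 0.77 would fall there, and 0.77/34 = 2.3% of the planned evaluable number.
- Extremes: none or all of the 5 fall after week 11, so between 34 and 29 participants contribute to the Evaluable change analysis.

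**The case against.** Several points on the other side stand.

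- Section 7.1 does not order discontinuation and 8.3.1 does not order Visit 4. Both are permissive. A reader might infer that 7.1 stops these participants outright; its wording does not say so. What remains is an unresolved ambiguity about a scan, not two opposed mandates.
- The advice to consult the study team is a central route that reduces variation between sites. It does not remove it, because a site that reads only one section sees nothing uncertain.
- A reader might infer that the primary analysis is at risk. For courses of at least 3 days it is not, as shown above.
- A reader might infer that losing late exacerbators flatters the drug. The documents do not show that they respond worst. Section 8.3 itself notes that exacerbations and their treatment may change airway inflammation, so a scan 7 to 14 days after OCS could look better or worse.
- A larger count is tempting. At the entry minimum of 2 exacerbations a year with no drug effect, 34 × 2 × 2/52 = 2.6 events (2.6/34 = 7.7%). That assumes that the drug does nothing, counts events rather than participants, and includes hospitalised cases, which are not in dispute. Even 0.77 may be high, because the gap of 5 also covers lower respiratory infections.
- The hospitalisation wording differs: 7.1 has an asthma-related event "requiring hospitalization for more than 24h or intubation", while 8.3.1 has an exacerbation or "infection requiring hospitalization (defined as an admission to an inpatient facility and/or" at least 24 hours of care. This is minor. The 7.1 list is not exhaustive, so adding infections in 8.3.1 is no contradiction, and the permissive 7.1 wording concerns the drug while the firmer 8.3.1 wording concerns the study.

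**Conclusion.** The inconsistency is real and should be corrected. Section 7.1 names a week-11 criterion that the section it cites does not contain, and 8.3.1 permits a delayed Visit 4 for the same non-hospitalised participant. Sections 1.1, 7 and 7.1 also disagree on whether a discontinued participant is withdrawn or remains in the study. Whether the week 13 scan is done can therefore depend on the section followed, subject to the study team's advice.

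The reach is limited to the change analyses in the Evaluable set, apart from the short-course case noted above. The expected size is about 0.8 participants, with an extreme range of 0 to 5. It rests on the assumption that the whole planned gap consists of such events spread evenly over 13 weeks; the documents give neither the timing nor the mix. The direction of any bias is unknown.

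**What to change.** Reconcile Sections 1.1, 6.5.1, 7, 7.1 and 8.3.1 so that one rule states whether a non-hospitalised participant treated with OCS between week 11 and Visit 4 has the Visit 4 assessments, and whether that participant remains in the study. Cover courses shorter than 3 days in the same rule. Align the hospitalisation wording in 7.1 and 8.3.1. Which clinical rule is kept is for the sponsor.

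The cost is protocol wording in five sections, with no added visits. Addendum Sections 1.1 and 2.14 already largely settle how participants with partial data are counted.
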